8.5. PSA (total) Response

If evaluable histopathology result for prostate cancer is not available and follow-up conventional imaging of the PyL-suspected lesion is not informative, subjects initiated on locoregional RT

alone (no concomitant ADT within 60 days following PyL PET/CT imaging) will be followed every 3 months for up to an additional 9 months post initiation of RT to assess PSA response to RT alone (without concomitant ADT administered during this time). A blood draw for PSA (total) will be obtained and sent to the central lab at each follow-up assessment. PSA response is defined by decline of $\geq 50\%$ from baseline PSA and must be confirmed within 4 weeks. Subjects will complete follow-up within the 9-month duration once PSA response is confirmed per the central lab.

To be evaluable for PSA response, applicable subjects should undergo RT with fields and target volumes adjusted based on presence of PyL-positive prostate bed, pelvic nodal, visceral or limited osseous metastases.

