- 7. If evaluable histopathology result for prostate cancer is not available and follow-up conventional imaging of the PyL-suspected lesion is not informative, subjects initiated on locoregional radiation therapy (RT) alone within 60 days following PyL PET/CT (with no concomitant ADT administered during this time) will be followed every 3 months (± 7 days), up to 9 months post-initiation of RT. PSA response (decline of ≥50% from baseline PSA) must be confirmed (two consecutive levels within 4 weeks) per central lab evaluation.
- 8. Pre-PyL Medical Management Questionnaire (MMQ) will be completed by the treating investigator for all subjects enrolled (who signed informed consent and met all eligibility criteria) in the study prior to Day 1.
- 9. Post-PyL MMQ will be completed by the treating investigator for all subjects who completed ¹⁸F-DCFPyL PET/CT imaging

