5.1.1. Primary Endpoint

The primary endpoint of the CLR is evaluated in a subset of Full Analysis Set (FAS) subjects with at least one positive lesion identified by ¹⁸F-DCPyL PET/CT imaging by the local reader and then evaluated against the composite truth standard by three independent, blinded central imaging readers. The CLR at the subject level is defined as the percentage of subjects for whom there is a one-to-one correspondence between localization of at least one lesion identified on ¹⁸F-DCFPyL PET/CT imaging (by central review) and the composite truth standard, which is defined either as:

- 1) evaluable local histopathology result for prostate cancer from surgery or biopsy performed within 60 days following PyL PET/CT, or
- 2) if evaluable histopathology is not available, informative conventional imaging (e.g., ¹⁸F-fluciclovine PET (preferred if was not performed at baseline) or choline PET; targeted MRI or CT; fluciclovine or choline PET) finding(s) of the anatomical correlate to the PyL-suspected lesion(s) within 60 days following PyL PET/CT, before locoregional or systemic treatment in is started, or
- 3) if neither of the above is available or informative, confirmed PSA response (PSA decline by ≥50% from baseline, confirmed within 4 weeks per central lab evaluation) post-RT (no concomitant ADT) that was initiated within 60 days following PyL PET/CT. PSA will be collected every 3 months, up to 9 months until PSA response (if achieved) is confirmed.

The CLR in percent is computed as $100 \times TP/(TP+FP)$; TP = true positives, FP = false positives.

A true positive (TP) result is defined as a subject with both a positive lesion(s) on ¹⁸F-DCFPyL PET/CT evaluated by at least one central reader and a positive result on the composite truth standard in the following order of importance:

- Positive finding for prostate cancer of a PyL-suspected lesion according to local histopathology (confirmed by at least one anatomical correlate will suffice to declare the PyL PET/CT assessed by the central reader defining a true positive), or
- Positive finding for prostate cancer of a PyL-suspected lesion upon follow-up correlative imaging by CT, MRI, whole body bone scan, NaF, fluciclovine or choline PET/CT

performed following PyL PET/CT (one confirmed anatomical correlate will suffice to declare the PyL PET/CT assessed by the central reader a true positive), or

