• PSA decreases by ≥50% from baseline following RT (without concomitant ADT) up to nine months following initiation of such treatment if the other two truth standards were not performed or did not provide evaluable results

False positives will be defined as subjects with positive lesion(s) on PyL PET/CT from at least one central reader who has the following negative findings for prostate cancer according to the composite truth standard:

- Negative finding for prostate cancer of a PyL-suspected lesion according to local histopathology, or
- Negative finding for all PyL positive lesion(s) upon follow-up correlative imaging performed following PyL PET/CT, or
- PSA does not decrease by ≥50% from baseline following RT (without concomitant ADT) up to 9 months following initiation of such treatment.

The CLR lesion location(s) will be matched with the CLR lesion location(s) identified by the composite truth standard to determine if colocalization is successful, denoting a true positive (TP) assessment. If a subject has more than one lesion identified by pathology or by correlative imaging, then at least one lesion must be successfully colocalized for the subject to be considered a TP. The anatomic regions and CLR lesion locations matched by laterality (right or left) where applicable are presented in Table 3. The pelvic lymph nodes are grouped together for analysis in alignment with the data collected in the PyL-2301 (OSPREY) study. Within the prostatic region and extra-pelvic lymph nodes, specific CLR lesion location groupings are further modified specific for PET/CT findings based on Prostate Cancer Molecular Imaging Standardized Evaluation (PROMISE)² intended to guide reproducibility, general applicability and clinical relevance.

Table 3: Lesion Locations and Anatomic Regions

Anatomic Region	CLR Lesion Locations
Prostatic	Prostate gland or prostate bed (including seminal vesicles)
Pelvic Lymph Nodes	 Right Pelvic (including Internal Iliac [Hypogastric], External Iliac, Common Iliac, Obturator) Left Pelvic (including Internal Iliac [Hypogastric], External Iliac, Common Iliac, Obturator) Other pelvic (including Rectal/perirectal and Presacral)

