Surgical pathology	Positive	Yes	TP
Surgical pathology	Positive	No	FP
Surgical pathology	Negative	Yes or No	FP

Progenics Pharmaceuticals, Inc. Statistical Analysis Plan: Protocol PyL3301

Composite Truth	Truth Standard	Central PyL	Subject Outcome
Standard Source	Location Result	Reader Location	~ u~jeet e ueeeme
		Match	
Surgical pathology	Unevaluable	Yes or No	Unevaluable, evaluate
			with another truth
			standard
Image guided biopsy,	Positive pathology	Yes	TP
needle or tissue	in the same		
sampling device in PyL	anatomic region as		
positive lesion	at least one PyL		
	positive lesion		
Image guided biopsy,	Negative pathology	Yes	FP
needle or tissue	in the same		
sampling device in PyL	anatomic region as		
positive lesion	at least one PyL		
* '1 11'	positive lesion	**	** 1 11 1
Image guided biopsy,	Positive or negative	Yes or No	Unevaluable, evaluate
needle or tissue	pathology in the		with another truth
sampling device not in	same anatomic		standard
PyL positive lesion	region as at least one		
	PyL positive lesion	271.	
Image guided biopsy,	Positive or negative	N/A	Unevaluable, evaluate
sampling method	pathology in the		with another truth
confirmation is not	same anatomic		standard
applicable or the	region as at least one		
confirmatory image is	PyL positive lesion		
unevaluable	C 1.: T :	3 7	TD
Correlative imaging	Correlative Imaging	Yes	TP
(Truth Panel assessment)	result positive	N.	ED
Correlative imaging	Correlative Imaging	No	FP
(Truth Panel assessment)	result positive	Vac	FP
Correlative imaging	Correlative Imaging	Yes	ГГ
(Truth Panel assessment)	result negative	Yes or No	Unavaluable avaluate
Correlative imaging (Truth Panel assessment)	Correlative Imaging unevaluable	i es oi no	Unevaluable, evaluate with another truth
(Truth Faller assessment)	unevaluable		standard
PSA response following	Observed ≥ 50%	N/A	Unevaluable
locoregional RT	decrease from	1N/A	Officialitable
locoregional K1	baseline up to 9		
	months from start of		
	RT, but response not		
	confirmed		
PSA response following	Radiation therapy	N/A	Unevaluable
locoregional RT	not directed to all	1 1/ / 1	Onevaluable
100010gioilai Ki	PyL suspected		
	lesions		
	10310113		

Statistical Analysis Plan: Protocol PyL3301

Composite Truth	Truth Standard	Central PyL	Subject Outcome
Standard Source	Location Result	Reader Location	
		Match	
PSA response following	Confirmed $\geq 50\%$	N/A	TP
locoregional RT	decrease from		
	baseline at or before		
	9 months from start		
	of RT		

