PSA response following	No observed $\geq 50\%$	N/A	FP
locoregional RT	decrease from		
	baseline up to 9		
	months from start of		
	RT, but PSA results		
	are available		

N/A: not applicable

Lesion mismatches are defined as False Positives due to the subject having a positive finding (by Central PyL read) on the PyL scan.

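### SAP 5.1.1 gives conflicting outcomes to a man whose 50% PSA fall is not confirmed, and Table 4 does not separate a failed repeat from a missing one

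*SAP*

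**What the plan says.** **Definition.** Item 3 of the composite truth standard (SAP 5.1.1; Protocol 8.1) requires a confirmed fall. SAP Table 2, note 7 states the rule: "PSA response (decline of ≥50% from baseline PSA) must be confirmed (two consecutive levels within 4 weeks) per central lab evaluation". Protocol 8.5 says that the decline is "from baseline PSA and must be confirmed within 4 weeks".

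**Text bullets.** The PSA bullet under true positives (SAP 5.1.1; Protocol 10.4.2.1) asks for a fall of at least 50% within 9 months of starting RT and does not mention confirmation. The matching false-positive bullet in the SAP is "PSA does not decrease by ≥50% from baseline following RT (without concomitant ADT) up to 9 months following initiation of such treatment". It does not mention confirmation either.

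**Table 4.** A confirmed fall is TP. The row for no observed fall, which contains "RT, but PSA results" being available, is FP. The row for an observed fall, containing "RT, but response not" confirmed, is Unevaluable. The unevaluable pathology and imaging rows send the subject on to another truth standard. This row does not, and PSA is the last standard in the hierarchy.

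**Use.** SAP 8.5.2.1 computes the CLR as TP/(TP+FP) over evaluable subjects for each reader. Success requires a lower 95% limit above 0.2 for at least two of three readers.

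**The concern.** Two different men share one Table 4 row. For the first, no repeat PSA was drawn within 4 weeks, so confirmation is missing. For the second, the repeat was drawn and showed a fall of less than 50%, so the confirmation test was done and failed. Unevaluable suits the first. The second has the data that the definition asks for and does not meet it, yet he leaves both numerator and denominator. One early low value also bars him from FP for good, whatever his later values show.

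Elsewhere in Table 4 a completed test with a negative result is FP: negative surgical pathology, negative in-lesion biopsy, negative correlative imaging. So is a positive surgical-pathology or imaging result at a non-matching location. A failed repeat PSA is the exception.

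At stake is the classification rule of the primary endpoint. Table 4 marks the reader's location match as not applicable for PSA rows, so the choice affects every reader who called the scan positive, not one reader in isolation.

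**Working it through.** **1. The plan's own figure.** Inputs from SAP 7.1: CLR 30%, lower 95% limit 20%, normal approximation.

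n = 1.96² × 0.30 × 0.70 / 0.10² = 80.67, rounded up to 81. This reproduces the stated 81 positive scans. Then 81/0.60 = 135 (stated 134) and 134/0.70 = 191.4, so 192 as stated. The design places the expected lower limit almost exactly on the success bound.

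**2. One man, three texts.** Take a man with an observed fall of at least 50%, a repeat within 4 weeks below 50%, and no confirmed response by 9 months.

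| Text | Outcome |
|---|---|
| TP bullet, SAP 5.1.1 and Protocol 10.4.2.1 | TP, read literally |
| Truth standard item 3 and Table 2, note 7 | No response |
| Table 4 | Unevaluable |

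**3. Direction.** Suppose 81 scored men include two such men, and 24 of the other 79 are TP. Wald lower limit = p − 1.96 × √(p(1−p)/n).

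| Scoring of the two men | CLR | Lower limit | Result |
|---|---|---|---|
| TP (literal bullet) | 26/81 = 32.1% | 21.9% | pass |
| Unevaluable (Table 4) | 24/79 = 30.4% | 20.2% | pass |
| FP (confirmed-response definition) | 24/81 = 29.6% | 19.7% | fail |

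Dropping one man only, 24/80 gives 19.96%, still a fail. Against the definition, Table 4 raises the CLR by the factor 1/(1−r), where r is the share of scored men with a refuted fall. Here r = 2/81, and (24/81)/(1 − 2/81) = 24/79.

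**4. Size when the evaluable number is held at 81.** Protocol 10.4.2 stops once the required number is evaluable, so dropped men would be replaced. The minimum pass is then 25/81, lower limit 20.8%. Counting k failed-repeat men as FP:

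| k | Proportion | Lower limit | Result |
|---|---|---|---|
| 1 | 25/82 | 20.52% | pass |
| 2 | 25/83 | 20.25% | pass |
| 3 | 25/84 | 19.98% | fail |

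**5. False-success rate for one reader.** Take a true CLR of 20% in the full 81+k men, with k non-TP men always dropped (exact binomial). For k = 3, P(X ≥ 25 of 84) = 2.1% with the men dropped, against P(X ≥ 26 of 84) = 1.1% with them kept. For k = 4, the figures are P(X ≥ 25 of 85) = 2.5% against P(X ≥ 26 of 85) = 1.3%. For k = 1 or 2 the threshold stays at 25 and the two rates are equal.

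**6. Sensitivity analyses (SAP 8.5.2.2).** The MAR imputation fills in unevaluable truth results within baseline PSA groups, so a failed confirmation is treated as missing and can be drawn as positive. The method-specific imputation names histopathology, Axumin, CT and MRI as pools, but not PSA. The tipping-point analysis shifts the response probability by up to −0.95, but for all missing and unevaluable subjects together.

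**The case against.** A reader might infer that the plan discards known negatives and so inflates the CLR in one direction. The documents do not support that as stated. The TP bullets omit confirmation, and against them Table 4 removes true positives and lowers the CLR (step 3). No text says that a failed confirmation is a negative truth result: the FP bullets and the FP row all require that no 50% fall occurred. Treating one value on each side of a threshold as indeterminate is a defensible third tier, and it was prespecified. The upward bias therefore holds only against the confirmed-response definition.

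The case is also narrow. PSA is used only when histopathology and imaging give no answer, with RT started within 60 days, without ADT, and directed to all suspected lesions. The man must then fail the repeat and not confirm later. The data to identify him may be incomplete: SAP Table 7 lists only the Month 3, 6 and 9 PSA visits, and SAP 8.6.4 ends PSA evaluation at the first 50% fall. The tipping-point analysis comes close to scoring all unevaluable men as FP, and the planned PSA and RT listings would allow rescoring.

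These limits stand. They do not remove the contradiction between the three texts or the merging of two cases in one row. The tipping-point analysis cannot isolate the failed-repeat men.

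**Conclusion.** The scoring rules for an unconfirmed PSA fall conflict and should be settled before database lock. Against the confirmed-response definition, excluding failed-repeat men removes only non-TPs and can only raise the CLR; against the TP bullet the same exclusion lowers it.

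The number of such men is not in the documents and may be zero; 0 to 4 is an assumption. Within that range the effect on the CLR is small in percentage points. It decides a reader's result only near the bound: two men if the scored set shrinks from 81 to 79, three if 81 evaluable men are reached by replacement. The one-reader false-success rate in step 5 stays at or below 2.5% up to four men. This is a specific defect worth correcting in the primary endpoint's scoring, but inflation has not been shown.

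**What to change.** 1. Split the Table 4 row. Observed fall of at least 50%, no repeat within 4 weeks and no later confirmed response: Unevaluable. Observed fall of at least 50%, repeat within 4 weeks showing a fall below 50%, and no confirmed response by 9 months from start of RT: FP.
2. Put confirmation into both the TP and the FP PSA bullets in SAP 5.1.1 and Protocol 10.4.2.1, with the missing-repeat case excepted from FP. Changing the FP bullet alone would leave the failed-repeat man meeting both definitions.
3. Reconcile SAP 8.6.4, which ends PSA evaluation at the first 50% fall, with Protocol 4.3.5.1 and 8.5, which continue until response is confirmed.
4. Report the CLR with failed-repeat men as FP and, as a sensitivity analysis, as Unevaluable.

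The cost is wording, one extra row of programming, and a CLR that may be slightly less favourable. The rescoring itself needs only the PSA values that were obtained; where no repeat exists, the man stays Unevaluable.

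### SAP Table 4 scores a confirmed PSA response as a true positive without requiring the central reader's lesion location to match the irradiated site

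*SAP*

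**What the plan says.** SAP 5.1.1 counts a subject towards CLR when "there is a one-to-one correspondence between localization of at least one lesion identified on" the PyL scan, by central review, and the composite truth standard. It then states: "The CLR lesion location(s) will be matched with the CLR lesion location(s) identified by the composite truth standard to determine if colocalization is successful", with success denoting a TP. SAP 8.5.2.1 repeats the location requirement for the primary analysis. Neither section makes an exception for PSA.

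The third tier of the truth standard is PSA response. A subject is TP if "PSA decreases by ≥50% from baseline following RT (without concomitant ADT) up to" nine months from the start of treatment, where the first two tiers were not done or not evaluable.

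In Table 4, every PSA row has N/A in the column for central reader location match. A confirmed response is TP and no observed response is FP. One further PSA row (the RT-coverage row) makes the subject unevaluable if RT did not cover every PyL-suspected lesion. Its match cell is also N/A. The note under the table reads: "Lesion mismatches are defined as False Positives due to the subject having a positive finding (by Central PyL read) on the PyL scan".

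Protocol 8.5 says that, to be evaluable for PSA response, subjects should undergo "RT with fields and target volumes adjusted based on presence of PyL-positive prostate bed, pelvic nodal, visceral or limited osseous metastases". The heading of Protocol 4.3.5.1 defines PyL-suspected lesions by the local PET/CT finding.

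**The concern.** A PSA fall carries no anatomical location. The only location available in this route is the site that was irradiated. That site is chosen with the local read in hand: SAP 5.1.2 says treatment-plan decisions rest on it. CLR, however, is scored separately for each blinded central reader.

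Suppose the local read shows prostate bed disease, RT goes there and PSA halves. A central reader who marked only a rib is scored TP under the confirmed-response row. Had the prostate bed been proven by surgical pathology instead, the same reader would be FP. At stake is the numerator of the primary endpoint, under a rule that applies to all three readers.

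The planned supporting analyses would not reveal this. The location regroupings in SAP 8.5.2.2 cannot change a score that uses no location. The imputations there address missing or unevaluable truth data only. The truth-standard subgroup in SAP 8.5.2.3 isolates the PSA stratum but does not show whether any reader's location matched.

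**Working it through.** **Step 1. Table 4 rows side by side.**

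| Truth source | Truth result | Reader location match | Outcome |
|---|---|---|---|
| Surgical pathology | Positive | No | FP |
| Correlative imaging | Positive | No | FP |
| PSA after RT | Confirmed fall of 50% or more | N/A | TP |
| PSA after RT | No such fall observed | N/A | FP |
| PSA after RT | RT missed a PyL-suspected lesion | N/A | Unevaluable |

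**Step 2. Two readings of the RT-coverage row**, for a central reader whose only lesion lies outside the irradiated site.

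- Row follows the local read: the subject passes it, so the reader is TP on response and FP on non-response.
- Row follows each central reader's own lesions: that reader is unevaluable either way. The gap closes, but the outcome then differs from the mismatch-is-FP note.

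**Step 3. The plan's own sample size** (SAP 7.1: CLR 30%, lower bound 20%, 60% positive scans, 30% non-evaluable).

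- Positive scans: 1.96² × 0.30 × 0.70 / 0.10² = 80.67, so 81.
- Total scans: 80.67 / 0.60 = 134.5 (stated 134).
- Subjects: 134 / 0.70 = 191.4, so 192. The stated figures reproduce.

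**Step 4. Success threshold at n = 81.** Lower limit = p − 1.96 × √(p(1 − p)/81), which must exceed 0.20 for at least two of three readers (SAP 8.5.2.1).

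- 24/81: 0.2963 − 0.0994 = 0.197, fails.
- 25/81: 0.3086 − 0.1006 = 0.208, passes.

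The exact binomial probability that a single reader reaches 25 TPs is 1.35% at a true CLR of 20% and 47.4% at 30%.

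**Step 5. Size if the row follows the local read.** Scored against mismatch = FP, the excess CLR is s × m × q. Here s is the PSA-route share of evaluable subjects, m the share of those whose reader location is outside the irradiated site, and q the response rate among them. All three are assumptions; the documents give none. The last column takes a location-matched CLR of 20%.

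| s | m | q | Excess CLR (points) | TPs of 81 | Single-reader success |
|---|---|---|---|---|---|
| 1% | 10% | 30% | 0.03 | 0.02 | 1.4% |
| 10% | 20% | 60% | 1.2 | 0.97 | 2.7% |
| 20% | 30% | 60% | 3.6 | 2.9 | 8.2% |
| 30% | 30% | 80% | 7.2 | 5.8 | 26.5% |

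Under this rule the excess cannot be negative, because non-responders are FP with or without a match. A scored CLR of 30% would become 28.8% in the second row and 22.8% in the last.

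**Step 6. If out-of-field readers are unevaluable instead**, the direction is not fixed. Take a scored CLR of 30% (24.3 TPs of 81), s = 20% and m = 30%, so 0.06 × 81 = 4.86 readings leave the denominator.

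- q = 60%: (24.3 − 2.92) / (81 − 4.86) = 28.1%.
- q = 20%: (24.3 − 0.97) / (81 − 4.86) = 30.6%.

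**The case against.** PSA response is openly declared as the last tier of the truth standard in both documents. It has no location to match, and Table 4 defines N/A as not applicable. The mismatch note can therefore be read as covering only rows where a match is assessed. The RT-coverage row, with Protocol 8.5, gives an indirect location check. Table 4 classifies scans positive by central review, so a per-reader reading of that row is available. The Imaging Review Charter, which SAP 5.1 cites for the read paradigm, may settle it but is not among the documents.

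The route is also a last resort: no evaluable histology, uninformative imaging, and RT without ADT begun within 60 days. Subjects still in follow-up at database lock become unevaluable (Protocol 10.4.2). Grouping the pelvic nodes in Table 3 makes mismatches rarer. CLR is tabulated by truth-standard category.

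Much of this stands. It rules out saying that the route has no location check at all, and it suggests that the affected number may be small. It does not remove the conflict. The general definition and the colocalization sentence carry no PSA exception. The RT-coverage row names no reader and consults no reader's locations, and the protocol's wording points to the local read.

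A further fair point is that the nearest analogues in Table 4, a biopsy device outside the PyL-positive lesion and RT that missed one, give unevaluable rather than FP. That is a reason to report both classifications.

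**Conclusion.** The point holds as an unresolved conflict within SAP 5.1.1. As written, a confirmed PSA response is TP wherever the central reader placed the lesion, unless the RT-coverage row is applied to each reader's own lesions, which the SAP does not say. If that row follows the local read, then measured against the SAP's mismatch-is-FP rule the gap can raise a reader's CLR but never lower it. The mid-range assumptions give 1.2 points, about 1 TP of 81. That decides a reader's result only near 24 versus 25 TPs.

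A reader might infer that CLR is inflated, or that the rule favours success under any scheme. The documents support neither. They give no PSA-route share, mismatch rate or response rate, and at a 1% share the excess stays below 0.25 point across the assumed ranges. If the row is applied per reader, this inflation largely disappears. If mismatches are unevaluable, CLR can move either way. The rule can also count against a reader: one who marks untreated disease outside the field is FP when PSA does not fall.

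The change is worth making before database lock. The sample-size figures are unaffected.

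**What to change.** 1. In Table 4, state whether the RT-coverage row refers to lesions on the local read or on each central reader's own read.
2. In the confirmed-response row, replace N/A with a per-reader match. Score TP only if at least one of that reader's CLR lesion locations lies in a recorded irradiated site. Otherwise score FP, as for positive surgical pathology or imaging without a match. Score unevaluable if the irradiated site is unknown or not recorded at Table 3 level. Word this to agree with item 1, so that no reading falls under two outcomes.
3. Add to SAP 8.5.2.2 a sensitivity CLR in which readers with no location in the irradiated site are unevaluable, for responders and non-responders alike, in line with the RT-coverage row.

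The cost is SAP wording and a small programming step, and CLR may come out slightly lower. One thing must be confirmed first. The appendix plans a locoregional RT listing (16.2.6.9) but shows only its title, so the sponsor should check that treated sites are captured with the location and laterality used in Table 3. The change leaves patient treatment, the PSA response definition and the follow-up schedule as they are.
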